16.4.2 Secondary Efficacy Analyses

A fixed sequence testing procedure will be used to control the overall level of significance for the analysis of the secondary endpoints of OS and ORR. If the primary analysis of PFS is statistically significant (p<0.0476), then OS will be analyzed using a two-sided test at the alpha=0.0476 level of significance. In addition, if the analysis of OS is statistically significant (p<00476), then ORR will be analyzed using a two-sided test at the alpha=0.0476 level of significance. However, if an earlier analysis is not statistically significant, the remaining analyses will be exploratory rather than confirmatory.

The secondary endpoint of OS is defined as time from randomization to death or to the date of last follow-up. The date of last follow-up confirming survival will be used as the censoring date for subjects who are alive and/or do not have a known date of death. The analysis of OS will be conducted using the two-sided log-rank test. Kaplan-Meier OS curves will be displayed by treatment arm. Median OS and percent OS at fixed time points will be estimated.

The secondary endpoint of ORR will be analyzed using Pearson's chi-square test. Overall response rate (ORR) is defined as the proportion of patients who have a partial or complete response to therapy according to RECIST 1.1. ORR will be reviewed 6 months after treatment with Vigil.

The analyses of all other secondary endpoints will be conducted using two-sided tests at the alpha=0.05 level of significance.

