- 8. Blood (PBMC) for immune function analysis (ELISPOT).
- 9. Plasma for immune function analysis (ctDNA).

Response Follow Up Assessments

If the study agent is discontinued (for reasons such as completion of all available doses of vaccine, intolerable toxicity, treatment interruption of more than 4 weeks, intercurrent illness, protocol deviation, at PI's discretion), the subject will be followed quarterly after the end of study visit until progression.

The following evaluations will be performed quarterly (every 3 months ±7 days) (unless otherwise specified):

- 1. A physical examination, including vital signs and body weight.
- 2. Assessment of concomitant medications taken.
- Radiological assessment of disease status with CT chest /abd/pelvis (MRI abd/pelvis may be substituted for CT abd/pelvis) must be collected. The methods used for prestudy assessments (e.g., CT or MRI) should be used throughout the study. If possible, the same equipment should be used each time.
- 4. A CBC with differential and platelet count.

- 5. Serum chemistries (creatinine, glucose, total protein, blood urea nitrogen (BUN), total carbon dioxide (CO2), albumin, total bilirubin, alkaline phosphatase, and aspartate transaminase (AST) and/or alanine transaminase (ALT)) and electrolytes (total calcium, chloride, potassium, sodium).
- 6. Blood collection for immune function analysis (ELISPOT) 3 months ±7 days from EOT and every 6 months ±7 days thereafter.
- 7. Assessment of Performance Status.

Long Term Follow Up

After progression, subjects and their physicians will be contacted quarterly for documentation of post study therapies and survival status.

As the intent-to-treat population includes all randomized patients, should a subject be randomized and choose to not receive any treatment on this study, the subject should be asked if he or she is willing to allow for survival follow up through phone call and/or physician contact quarterly. This follow up would include any anti-cancer therapies received and survival status information.

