16.0 STATISTICAL CONSIDERATIONS

16.1 Sample Size Justification

This is an open label randomized controlled Phase III clinical trial. Information concerning the predicted survival of the control group is limited, based on rarity of disease and few published reports. However expert advisors in the EWS field estimate a conservative one-year survival rate of 25% in the chemotherapy control group. The one-year survival rate of 60% in the Vigil treated group is estimated from EWS patients treated on the Vigil phase 1 protocol. These estimates correspond to a hazard ratio (HR) of 0.383 favoring Vigil over control.

Assuming 1:1 randomization and the use of a two-sided log rank test at the alpha=0.0476 level of significance, 67 events will provide 90% power to detect an PFS HR of 0.45. Assuming a Group B (control group) median PFS of 6 months, a one-year accrual period, and a six-month follow-up period after randomization of the last subject, it is estimated that the total sample size (number of subjects) required to achieve 67 events is 114 (57 patients in each arm).

An unblinded interim analysis will be conducted by an independent data monitoring committee (IDMC) when 40 PFS events have occurred. Based on the results of this interim analysis, the planned sample size may be increased to 120 events. If the sample size is increased to 120 events, then the study will have approximately 90% power to detect a true HR of 0.55. Note that if the sample size is increased to 120 events, then the accrual period will be extended to 24 months, with a 6-month follow-up period after randomization of the last patient. Under these assumptions, it is estimated that approximately 164 patients will need to be randomized in order to achieve 120 events. Section 16.6 provides further details.

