16.6 Interim Analysis

An interim analysis for efficacy, futility, and potential sample size re-estimation will be conducted by an independent data monitoring committee (IDMC) when 40 PFS events have been achieved (60% information fraction). Based on the Lan-DeMets method for group sequential trials using O'Brien-Fleming boundaries (Reboussin, DeMets et al. 2000), the levels of significance for the interim and final analyses are alpha=0.00762 and alpha=0.0476, respectively.

Based on the results of the interim analysis, the IDMC will make one of the following four recommendations to the sponsor:

- Terminate the study for efficacy (p<0.00762 at the interim analysis);
- Continue the study as planned;
- Increase the sample size to 120 events;
- Terminate the study for futility.

Provided that the IDMC does not recommend terminating the study early for efficacy, the conditional power of the planned final analysis at 67 events will be computed using the methodology of (Jennison and Turnbull 2000) under the assumption that the observed hazard ratio at the interim analysis represents the true effect. In terms of the HR observed at the interim analysis, these rules can be translated (approximately) as follows:

- If the HR is less than 0.43, terminate for efficacy
- If the HR is in the range from 0.43 to 0.51, continue as planned.
- If the HR is in the range from 0.51 to 0.61 (i.e., conditional power in the range from 50% to 80%), increase the sample size to 120 events.
- If the HR is greater than 0.61 (i.e., conditional power less than 50%), terminate for futility.

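### OS has no boundary, death count or analysis date of its own, so the fixed sequence does not strictly control OS error across the two PFS looks

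*Protocol*

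**What the plan says.** Protocol 16.4.2 and SAP 8.1.2 say that a fixed sequence controls the overall level for OS and ORR. If PFS is significant at p below 0.0476, "then OS will be analyzed using a two-sided test at the alpha=0.0476 level of significance". ORR follows at the same level only if OS is significant; after a miss, the remaining tests are exploratory. On method, the protocol says: "The analysis of OS will be conducted using the two-sided log-rank test".

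Protocol 16.6 and SAP 8.3 give PFS two looks, at 40 and 67 events. For these, "the levels of significance for the interim and final analyses are alpha=0.00762 and alpha=0.0476, respectively", and the study may be terminated for efficacy at the first.

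Neither document gives OS an alpha-spending function, a number of deaths or an analysis date. Neither says whether OS is tested at an interim stop, whether it is tested only once, or whether it may be retested later. Survival data do continue to accrue under Protocol 9.0: "After progression, subjects and their physicians will be contacted quarterly for documentation of post study therapies and survival status".

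**The concern.** A fixed sequence protects a second endpoint when each endpoint is tested at one planned analysis. Here the look at which the sequence opens depends on the PFS data, and those data are correlated with OS because deaths count as PFS events. Testing OS at its full level at a look chosen in this way gives it two chances to be favoured by a good run in the same patients. To keep the stated control, OS needs a boundary of its own.

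Maturity is the second issue. If the confirmatory OS test is run at an interim stop, it uses few deaths, and a miss also removes ORR from the confirmatory sequence. If OS is instead tested at the stop and again later, no adjustment is written for the repetition.

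**Working it through.** **1. The plan's own figures.** The protocol states that "67 events will provide 90% power to detect an PFS HR of 0.45". Schoenfeld's formula gives D = 4(1.981 + 1.282)² / (ln 0.45)² = 66.8, so 67 is reproduced. O'Brien-Fleming-type spending at information fraction 0.60, with 0.025 per tail, spends 2[1 − Φ(2.241/√0.60)] = 0.0038 per tail. That is 0.0076 two-sided, matching 0.00762 (z = 2.668). The interim boundary in hazard-ratio terms is exp(−2 × 2.668/√40) = 0.43, also as stated.

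**2. Chance of an interim efficacy stop at the design effect.** Φ(√40 × 0.7985/2 − 2.668) = Φ(−0.143) = 0.44.

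**3. Error of a single OS test at the look where PFS succeeds.** I simulated joint normal log-rank statistics for PFS and OS at both looks (1 million draws per cell, simulation error about 0.0002). OS has no effect, the PFS effect is varied, and OS is tested at z = 1.981. The PFS-OS correlation and the OS information fraction at the interim are assumptions. The nominal one-sided rate is 0.0476/2 = 0.0238.

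| Correlation | Max. false OS benefit, OS fraction 0.4 | 0.5 | 0.6 |
|---|---|---|---|
| 0.3 | 0.026 | 0.025 | 0.025 |
| 0.5 | 0.027 | 0.027 | 0.026 |
| 0.7 | 0.031 | 0.029 | 0.028 |
| 0.8 | 0.032 | 0.031 | 0.029 |

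These are maxima over the PFS effect. At the design hazard ratio of 0.45 the rate is about 0.025 to 0.027. The two-sided error over the same grid is at most 0.047.

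**4. OS tested at both looks at 0.0476, unadjusted.** The maximum two-sided error is about 0.07 to 0.08 for correlations 0.3 to 0.8, and about 0.062 at correlation 1. These maxima arise with strong PFS effects; at the design effect the error is about 0.042 to 0.057 for correlations 0.3 to 0.8.

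**5. Deaths at an interim stop.** Take uniform accrual of 57 per arm over 12 months and exponential times. Expected events per arm at T ≤ 12 months are (57/12) × [T − (1 − e^(−λT))/λ]. With a control median PFS of 6 months and hazard ratio 0.45, 40 PFS events fall at T = 11.9 months. Expected deaths at that time:
- One-year survival 25% and 60% (Protocol 16.1; λ = 0.1155 and 0.0426): 25.7 + 12.1 = 37.8.
- One-year survival 43% in both arms (the first-relapse series in Protocol 1.2): 36.3.
- 43% in control with an OS hazard ratio of 0.383 to 0.45: 26 to 28.

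The value of 38 is near a ceiling. One-year survival of 25% implies a control median OS of 12 × ln 2/ln 4 = 6.0 months, equal to the assumed control median PFS. For only 13 to 20 deaths, pooled one-year survival would have to be about 78% to 67%; the documents give no such figure.

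**6. OS power at that stop.** Power = Φ(√D × |ln HR|/2 − 1.981).

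| Deaths | HR 0.6 (assumed) | HR 0.45 | Observed HR needed |
|---|---|---|---|
| 13 | 14% | 29% | 0.33 |
| 20 | 20% | 42% | 0.41 |
| 26 | 25% | 52% | 0.46 |
| 38 | 34% | 68% | 0.53 |

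**7. With separate OS spending (total two-sided 0.05).** At an OS information fraction of 0.60 the levels are 0.0076 and 0.0476; at 0.53 they are 0.0042 and 0.0487. A single test at the look where PFS succeeds then has a false OS-benefit rate of at most 0.025 for every correlation from 0 to 1. Testing at both looks keeps two-sided error at or below 0.050.

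**The case against.** The strongest reply is that the gate is written for the primary PFS analysis at 0.0476, which is the final-look level. On that reading no OS test is placed at the interim, and open-ended quarterly survival follow-up leaves room for a mature one. This stands in part: a reader might infer a rule that OS is tested once, at whichever look PFS succeeds, but the documents contain no such rule. It does not close the gap. After an interim efficacy stop, the documents do not say whether a later primary PFS analysis follows, so either OS has no confirmatory test or the interim success opens it. The plan does not say which.

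Second, the planned OS test is two-sided. A reader might infer from the missing boundary that OS error exceeds 0.0476. With a single test it does not, apart from the extreme of correlation 1 with no PFS effect, where PFS's own 0.05 is the bound. The excess is confined to the benefit direction and is small at the design effect, especially against 0.025, the one-sided half of 0.05. This objection stands as to size. It does not restore strict control, because a false claim of benefit is the error that matters.

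Third, waiting for deaths may not bring proportionate power. Group B may cross over to Vigil after progression (Protocol 10.0), and censoring at cross-over is only a sensitivity analysis. That is fair, and it is why no later-look power is claimed here. It is also a reason to settle the OS timing in advance.

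**Conclusion.** The concern holds in a limited form. The stated control of the overall level does not strictly extend to OS, because OS has no boundary or timing of its own while the PFS gate can open at two looks. With a single OS test, the benefit-direction rate can reach about 0.025 to 0.032 against 0.0238, for an assumed correlation of 0.3 to 0.8 and an OS information fraction of 0.4 to 0.6. Larger inflation requires unadjusted repeat testing, which the plan neither schedules nor excludes.

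The maturity problem holds across the whole range of death counts. Even 38 deaths give about one chance in three of detecting an assumed hazard ratio of 0.6. A reader might go further and conclude that the only OS test will be spent on 13 to 20 deaths, leaving nothing confirmatory to say about survival. The documents do not support that: their own survival rates give 26 to 38 deaths, and they do not make an interim OS test the only one. All these figures refer to the 67-event design.

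**What to change.** Amend Protocol 16.4.2 and SAP 8.1.2 before the interim is unblinded:
- Give OS its own Lan-DeMets O'Brien-Fleming-type spending function, with information measured in deaths and a total two-sided level of 0.05.
- Place one OS look at the analysis where PFS succeeds, and a final OS test at a pre-stated number of deaths or a fixed time after PFS success. State that this final test goes ahead after an interim efficacy stop.
- Keep the existing rule that ORR is tested only after OS succeeds.
- Remove the competing 0.05 level for secondary analyses in SAP 4.2 and 8.1.2 as it applies to OS and ORR.

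The survival follow-up already planned supplies the data, so no new visits are needed. The costs are later confirmatory OS and ORR results, a stricter first OS look than 0.0476, and possible dilution of the later OS contrast by Group B cross-over. Protocol as well as SAP wording must change; Protocol 11.5 requires a formal amendment for changes that affect study design.

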6.2 Tissue Procurement Inclusion Criteria

Subjects will be eligible for tissue procurement for the Vigil manufacturing process, if they meet all of the following criteria:

- 1. Histologically confirmed Ewing's Sarcoma Family of Tumors (ESFT).
- 2. Age ≥ 2 years.
- 3. Estimated survival \geq 6 months.
- 4. Evidence of EWS translocation by FISH or RT-PCR or Next Generation Sequencing (NGS). If available, NGS sequencing report should be submitted to Gradalis.
- 5. Recurrence or refractory to 1 line of systemic chemotherapy including but not limited to doxorubicin, vincristine and ifosfamide.
- 6. Planned standard of care surgical procedure (e.g., tumor biopsy or palliative resection or thoracentesis) and expected availability of a cumulative soft-tissue mass of ~10-30 grams tissue ("grape" to "golf-ball" size / approximate 2 cm total diameter on imaging) and/or pleural fluid estimated volume ≥ 500mL (from a primary or secondary thoracentesis, yielding in a high volume of tumor cells) for immunotherapy manufacture.
- 7. Tumor intended for immunotherapy manufacture is not embedded in bone and does not contain luminal tissue (e.g. bowel, ureter, bile duct).
- 8. Ability to understand and the willingness to sign a written protocol specific informed consent for tissue harvest or a parental/guardian informed consent and pediatric assent when appropriate.

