9.0 SCHEDULE OF ASSESSMENTS

Pre-study Assessments / Surgery Pre-Screening

The following evaluations will be performed within 4 weeks of tumor procurement (unless otherwise specified):

- 1. A signed Informed Consent Form for tissue harvest must be obtained.
- 2. It has been confirmed that the subject meets all tissue procurement inclusion criteria and none of the exclusion criteria.
- 3. A complete medical history must be obtained.
- 4. A physical examination must be obtained.

- 5. A complete blood count (CBC) with differential and platelet count must be performed. (HIV and hepatitis testing is not required if the subject has no medical history of HIV).
- 6. Routine pre-operative serum chemistries (including, but not limited to creatinine, total bilirubin, alkaline phosphatase, and aspartate transaminase (AST) and/or alanine transaminase (ALT).
- 7. Blood collection for immune function analysis will be obtained at tissue harvest. (≤1 week of tissue procurement)
- 8. Plasma collection for immune function analysis (ctDNA) (≤1 week of tissue procurement)

Screening Assessments / Protocol Screening

The following evaluations will be performed on all subjects within 2 weeks of Cycle 1 (unless otherwise specified):

- 1. A signed protocol specific Informed Consent Form must be obtained.
- 2. It has been confirmed that the subject meets all inclusion criteria and none of the exclusion criteria.
- 3. A physical examination (including vital signs, height, temperature and body weight) must be obtained.
- 4. Assessment of concomitant medications
- 5. Assessment of PS on the Karnofsky or Lansky scale (see Appendix A) must be obtained.
- 6. Radiological assessment of disease status with computed tomography (CT) chest /abdomen/pelvis (magnetic resonance imaging (MRI) abd/pelvis may be substituted for CT abd/pelvis) within 4 weeks of Cycle 1. The methods used for prestudy assessments (e.g., CT or MRI) should be used throughout the study. If possible, the same equipment should be used each time. Radiographic assessments must be from after the tissue harvest for vaccine manufacture to ensure true baseline disease status is captured. Images must be uploaded into WorldPro or submitted to WorldCare.
- 7. A complete blood count (CBC) with differential and platelet count must be performed. (HIV and hepatitis testing is not required if the subject has no medical history of HIV).

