16.3 Analysis Populations

The intent-to-treat (ITT) population will include all randomized subjects. All efficacy analyses will be completed in the ITT population.

The Safety population will include all patients who receive study treatment and patients will be analyzed according to actual treatment received. All safety analyses will be completed in the Safety population.

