8.1.2 Secondary Efficacy Analyses

A fixed sequence testing procedure will be used to control the overall level of significance for the analysis of the secondary endpoints of OS and ORR. If the primary analysis of PFS is statistically significant (p<0.0476), then OS will be analyzed using a two-sided test at the alpha=0.0476 level of significance. In addition, if the analysis of OS is statistically significant (p<00476), then ORR will be analyzed using a two-sided test at the alpha=0.0476 level of significance. However, if an earlier analysis is not statistically significant, the remaining analyses will be exploratory rather than confirmatory.

The secondary endpoint of OS is defined as time from randomization to death or to the date of last follow-up. The date of last follow-up confirming survival will be used as the censoring date for subjects who are alive and/or do not have a known date of death. The analysis of OS will be conducted using the log rank test. Kaplan-Meier OS curves will be displayed by treatment arm. Median OS and percent OS at fixed time points will be estimated.

The secondary endpoint of ORR will be analyzed using Pearson's chi-square test. Overall response rate (ORR) is defined as the proportion of patients who have prolonged stable disease or a partial or complete response to therapy according to RECIST 1.1. ORR will be reviewed 6 months after treatment with Vigil.

The secondary analysis of all secondary endpoints will be conducted using two-sided tests at the alpha=0.05 level of significance.

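### ORR is tested in all randomised patients although entry requires no measurable disease, so the response rate and the arm difference are diluted by an unknown amount

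*Protocol*

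**What the plan says.** **Endpoint.** Protocol 16.4.2 defines the rate by partial or complete response only: "Overall response rate (ORR) is defined as the proportion of patients who have a partial or complete response to therapy according to RECIST 1.1". SAP 8.1.2 differs and counts the "proportion of patients who have prolonged stable disease or a partial or complete response to therapy according to RECIST 1.1". Both documents use the same test: "The secondary endpoint of ORR will be analyzed using Pearson's chi-square test".

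**Denominator.** Protocol 16.3: "The intent-to-treat (ITT) population will include all randomized subjects", and "All efficacy analyses will be completed in the ITT population". SAP 8.0 says the same. Neither document defines a response-evaluable set or a rule for patients without target lesions. Protocol 6.1 speaks of 114 evaluable subjects, but the term is undefined and no analysis set uses it.

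**Position.** Protocol 16.4.2: "A fixed sequence testing procedure will be used to control the overall level of significance for the analysis of the secondary endpoints of OS and" (this endpoint is named last in the sentence). ORR comes third, after PFS and OS, at two-sided alpha 0.0476.

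**Entry.** Protocol 6.2 requires a "Planned standard of care surgical procedure (e.g., tumor biopsy or palliative resection or thoracentesis") that is expected to yield about 10 to 30 g of tumour and/or at least 500 mL of pleural fluid. No numbered criterion in Protocol 6.2 to 6.5 concerns measurable or residual disease. Protocol 5.0 describes the population as metastatic, but no criterion carries that word, and metastatic disease need not be measurable.

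**Baseline scan.** Protocol 9.0: "Radiographic assessments must be from after the tissue harvest for vaccine manufacture to ensure true baseline disease status is captured".

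**The concern.** Entry depends on removing tumour or draining fluid, and baseline is whatever remains afterwards. A patient whose only measurable lesion was resected, or whose material came from an effusion, can be randomised. With no residual disease there is nothing to respond. With only non-measurable disease a partial response is impossible, because it is judged on measured target lesions, though a complete response is not.

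Under the protocol definition the first group counts as non-responders in both arms by construction, and the second can succeed by one route only. At stake are an understated ORR, an understated difference and lower power. Without a rule, the classification of these patients might also be settled after data from an open-label trial have been seen.

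**Working it through.** **The plan's own figure.** The documents give no power or target rate for ORR; only PFS is sized. Events = 4(1.981 + 1.282)² / (ln 0.45)² = 42.58 / 0.6376 = 66.8, so 67, as stated. With exponential PFS, a 6-month control median, 12 months of uniform accrual and 6 months of follow-up, the event probabilities are 0.729 and 0.455, mean 0.592. Then N = 67 / 0.592 = 113, against 114 stated. The 57 per arm used below is therefore the plan's own number.

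**Inputs for ORR.** From the documents: 57 per arm and two-sided alpha 0.0476 (z = 1.981). Assumed, because the documents give none of them: the share q without measurable disease, the true rates p1 and p2 in measurable patients, and the relative response rate h in the others (0 = never respond, 0.5 = half the rate), with q and h equal in both arms.

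**Formulas.**
- All randomised: each rate becomes p(1 − q + qh), with n = 57 per arm.
- Measurable only: rates stay p, with n = 57(1 − q) per arm.
- Power = Φ[(d − 1.981·s0) / s1], where d is the difference between the rates, s0 = √(2·p̄(1 − p̄)/n) and s1 = √((p1(1 − p1) + p2(1 − p2))/n).

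**One case in full: 30% vs 60%, q = 20%.**
- All randomised, h = 0: rates 24% and 48%, s0 = √(2 × 0.36 × 0.64/57) = 0.0899, s1 = √((0.1824 + 0.2496)/57) = 0.0871. Power = Φ[(0.24 − 0.1781)/0.0871] = Φ(0.71) = 76%.
- Measurable only: n = 45.6, s0 = √(2 × 0.45 × 0.55/45.6) = 0.1042, s1 = √((0.21 + 0.24)/45.6) = 0.0993. Power = Φ[(0.30 − 0.2064)/0.0993] = Φ(0.94) = 83%.
- All randomised, h = 0.5: rates 27% and 54%, power 84%.

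| True ORR | q | All randomised, h = 0 | Measurable only | All randomised, h = 0.5 |
|---|---|---|---|---|
| 30% vs 60% | 5% | 87% | 89% | 89% |
| 30% vs 60% | 10% | 84% | 87% | 87% |
| 30% vs 60% | 20% | 76% | 83% | 84% |
| 30% vs 60% | 30% | 67% | 77% | 80% |
| 40% vs 68% | 20% | 67% | 77% | 77% |
| 63% vs 85% | 5% | 68% | 74% | 72% |
| 63% vs 85% | 20% | 47% | 67% | 60.5% |

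The 63% is a response rate that Protocol 1.3 cites for irinotecan with temozolomide; the 85% paired with it is an assumption. With every patient able to respond, power is 90%, 86% and 76% for the three pairs of rates.

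**Type I error.** In a simulation of 200,000 trials per setting, with equal rates of 30% or 63% in both arms, h = 0 and q from 0 to 30%, the all-randomised chi-square test rejected in 4.7% to 5.1% of trials. Dilution does not create false positives.

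All these powers concern the ORR test once it is reached, that is, after both PFS and OS have been significant.

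**The case against.** The strongest reply is that all-randomised ORR is a valid, conservative choice and that the loss is hypothetical. Much of this stands.

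- The share q has no basis in the documents. Biopsy, palliative resection and thoracentesis do not imply clearance of disease, and the population is described as metastatic. At q = 5% the loss in the 30% vs 60% case is about one and a half points.
- A reader might infer that every patient without measurable disease is a certain failure. That holds only for those with no residual disease. If the whole group responds at half the rate, restriction gains nothing at 30% vs 60% or 40% vs 68%, and costs about 3 points at 30% vs 60% with q = 30%. About 6 points of gain remain at 63% vs 85% with q = 20%.
- Under the SAP definition, a patient without measurable disease who stays stable might count as a success. Automatic failure is therefore established for the protocol definition only, and the conflict between the two definitions needs settling in any case.
- A reader might also infer that the trial's ORR cannot be compared with the 63% and 68.1% in Protocol 1.3. The documents do not state the denominators of those studies, so this cannot be concluded.
- A measurable-disease set can itself go wrong. Protocol 9.0 times the scan from Cycle 1 and SAP 12.1.1 from registration, neither from randomisation. The trial is open label, and SAP 12.1 provides both local and central reads. Membership decided by an unblinded local read after allocation would weaken the protection that the full set gives.

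What does not stand is that nothing need be done. The plan leaves these patients' classification unstated in a test that it calls confirmatory.

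**Conclusion.** The gap is real and of modest, unknown size. Under the protocol's definition, patients with no disease at baseline are non-responders by construction, and those with only non-measurable disease lose one of the two ways to respond. Given no response in this group and 30% vs 60% in the rest, the loss against a measurable-only analysis is about 1 to 3 points at q = 5% to 10% and about 7 to 10 points at q = 20% to 30%. It is larger where true rates are high (19 points at 63% vs 85%, q = 20%) and can vanish or reverse if the group responds at half the rate.

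The documents do not support a finding of bias towards either arm, of inflated type I error, or of a shortfall from a planned ORR power, since none was planned. Randomisation balances q between arms on average; measurability is not a stratification factor, so chance imbalance remains possible. PFS and OS are not affected by this point. It is worth correcting because the remedy is cheap and must be fixed before data are seen.

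**What to change.** In Protocol 16.3 and 16.4.2 and SAP 8.0 and 8.1.2:

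1. Define the ORR analysis set as all randomised patients with at least one RECIST 1.1 measurable lesion on the post-harvest, pre-treatment scan, as determined by the planned central read, blind to arm. Analyse as randomised, and count patients without post-baseline assessments as non-responders.
2. Keep ORR in all randomised patients as a supportive analysis. Report per arm the number without measurable disease, any complete responses among them, and the number with no baseline scan.
3. Remove prolonged stable disease from the SAP definition, so that it matches the protocol's partial-or-complete response.
4. Make the baseline-scan timing in SAP 12.1.1 agree with Protocol 9.0.

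The cost is a few sentences in each document. Baseline images already go to third-party review (Protocol 9.0 and 12.1), so no new data are needed. The downside is a smaller denominator, about 46 per arm at q = 20%, which the measurable-only powers already reflect. PFS and OS stay in the full ITT set.
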